Muscle biopsies of the quadriceps muscle (on the same side as the leg blood flow assessment) will be performed at a separate visit at least 3 days remote from the maximal exercise test, using a modified Bergstrom needle as has been extensively utilized by [name] group, to directly assess the skeletal muscle mitochondrial oxidative capacity component of peripheral O_2 utilization.²⁶⁻²⁸ High-resolution respirometry will be performed on mitochondria freshly isolated from the biopsy sample. Approximately 100 mg of tissue will be homogenized, and mitochondria separated using differential centrifugation. Mitochondria are added to a 2 ml chamber (Oxygraph-2K, Orobos) and allowed to equilibrate. Glutamate (10 mM) and malate (2 mM) are added to stimulate State 2 respiration specific to Complex I, then ADP is added at saturating concentrations (2.5 mM) to induce State 3 respiration of Complex I. Cytochrome-c is added to verify mitochondrial membrane integrity. Succinate (10 mM) is added to stimulate State 3 respiration through Complex I+II and then rotenone (0.5 μ M) is added to inhibit complex I for State 3 respiration specific to Complex II. State 4 respiration (Leak) is induced by addition of oligomycin (2 μ g/ μ l) then the proton gradient is dissipated by sequential titration of 0.05 mM carbonylcyanide-4-(trifluoromethoxy)-phenylhydrazone to induce uncoupled respiration. Protein content of isolated mitochondrial is determined using a commercially available kit (DC Protein Assay, Bio-Rad). Mitochondrial respiration measures will be normalized to tissue wet weight (reflective of mitochondrial content) and mitochondrial protein (reflective of mitochondrial protein quality). *Maximum mitochondrial respiration* for the respiratory complexes (Complex I+II) will be reported in pmol O_2 /ml/sec (per tissue content) and in pmol O_2 / μ g mito/sec (per mitochondrial protein content). *Mitochondrial efficiency* will be calculated as Respiratory Control Ratio (State 3/State 4).^{28,29}

Isolated quadriceps muscle mitochondria will be treated with glutamate and malate, and H_2O_2 emission (ROS) will be measured using Amplex Red oxidation (p mol/s/ μ g protein).³⁰

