As described above we anticipate that patients with PAH-ILD will have impaired Q_c reserve with activity (exercise-rest Q_c <80% predicted based on normal measured change in VO₂ - the normal increase in Q_c being 6 ml/min per 1 ml/min in VO₂)³¹ during exercise at 20 watts for 5 minutes, which will improve following inhaled treprostinil. The degree of Q_c improvement during exertion with inhaled treprostinil will likely predict an improvement in NYHA class with 3 months of inhaled treprostinil as chronic therapy. Exploratory analyses of changes in other exertional pulmonary, central and peripheral indices with symptom improvement will also be performed.

J. Description of potential challenges and possible approaches to address them

Some patients with PAH-ILD may be O₂ dependent which precludes a face mask to directly measure gas exchange and VO₂ at the mouth. In these patients we will measure Q_c using the thermodilution method during rest and exercise which is the most accurate method in patients on supplemental O₂ therapy.³⁴ Another potential problem is failure to enroll the target number of participants for the study. This is an unlikely problem because the Mayo Clinic Pulmonary Hypertension program follows more than 300 adult PAH patients who are evaluated in the outpatient clinic annually. For the approximately 50 PAH patients a year who are newly initiating or intensifying therapy, cardiac catheterization is the standard of care, and ILD-PAH is one of the fastest growing areas in our clinical practice with our large ILD practice. In our laboratory, exercise RHC is routinely used in the evaluation of PAH and will provide no additional cost to this proposal. I also practice primarily in the PH clinic and cardiac catheterization hemodynamic lab which will maximize patient recruitment and feasibility. Importantly we have a successful track record of recruiting more than 15 patients a year for acute hemodynamic exercise studies in four completed^{14,15,35,36} and three ongoing studies of patients with pulmonary hypertension during exercise which do not overlap with this proposal. We will additionally provide remuneration to patients for their travel expenses and time to participate. Additional challenges relate to the acute effects of exercise on mitochondrial respiration that may confound the biopsy results. To mitigate this, the biopsy will be performed at

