least 3 days after the initial exercise study. All baseline hemodynamic and peripheral data will be interpreted and analyzed blinded to subsequent symptom response

Inclusion Criteria for PAH

- PAH due to Interstitial Lung disease being considered for inhaled treprostinil
- Resting right heart catheterization with mean pulmonary artery pressure>20 mmHg and PVR> 3 Wood units
- >=18 years of age

Exclusion criteria

- Inability to exercise
- Females who are pregnant

Inclusion Criteria for controls

- >=18 years of age
- No known heart failure, pulmonary hypertension, lung disease or muscular disease
- Ability to exercise
- No bleeding abnormalities

Schedule of assessments:

For PAH ILD patients

Visit 1

- Baseline assessments of PAH SYMPACT and SF-36 for quality of life will be performed
- Patients will undergo clinically indicated right heart catheterization with exercise as per clinical practice with internal jugular approach and right radial arterial line. Exercise will be performed up to 20 watts for 5 minutes.
- After exercising to 20 watts for 5 minutes, patients will be administered 32 mcg of inhaled treprostinil followed by 30 minutes of rest in the catheterization laboratory
- Repeat exercise up to 20 watts for 5 minutes will be performed after 30 minutes of rest.
- Simultaneous echocardiogram will be performed at rest and exercise.
- 10 ml of blood at rest and 5 ml with exercise will be stored at rest and exercise from the baseline phase. In addition high sensitivity troponin levels will be measured at rest and exercise before and after inhaled treprostinil.
- Following the second exercise phase Visit 1 will be completed

Visit 2 (optional muscle biopsy)

- Patients will be offered an optional muscle biopsy component with percutaneous needle biopsy in [name] laboratory for skeletal muscle mitochondrial assessment. Remuneration of \$200 will be provided for completion of the muscle biopsy component

Virtual Visit 3 (end point assessment)

- Patients will be contacted remotely at 4 months to mail back repeat PAH SYMPACT and SF-36 questionnaires for end point assessment of quality of life. Patients will be contacted by phone to assess NYHA class by Principal Investigator.

PAH-ILD subjects

Study Activity	Visit 1 Day 0	Visit 2 Day 3-14 (+/-)	Virtual Visit 3 Month 4 (+/- 14 days)
Informed Consent ¹	X		
Right Heart Catheterization	X		
Treprostinil Test dose	X		

Echocardiogram ²	X		
Troponin ³	X		
Research blood ⁴	X		
Questionnaires ⁵	X		X

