Percutaneous skeletal muscle biopsy of the vastus lateralis muscle will be performed at a separate visit 1-14 days after the baseline qualifying RHC. Risks include pain, bleeding/bruising, infection, scarring. Patients will hold anticoagulation for this procedure to minimize the risk of bleeding. The procedure will be completed by a trained RN, MD or PhD. The participant is given complete instructions and expectations prior to the procedure both on the consent form and verbally. To ease pain, 2% Lidocaine is buffered with 8.4% sodium bicarbonate to decrease acidity of the lidocaine. Tylenol is ordered as needed for pain. The participant is instructed to gently flex leg at least every 30 minutes to decrease stiffness in the leg. To minimize bleeding/bruising, the participant is asked not to use aspirin or ibuprofen for 3 days prior to and post biopsy. Careful choice of biopsy site avoids veins and arteries. Pressure is held at least 10 minutes after the biopsy or until hemostasis occurs. An ace wrap applied. An ice pack is advised if bruising occurs. Patient education on post biopsy care is given verbally along with written instructions. To minimize the risk of infection, biopsies are performed using aseptic technique. The participant is educated on signs and symptoms of infection with instructions to call the study team (numbers provided) with any signs of infection or other concerns. To minimize the risk of scarring, the incision is made no larger than is needed to insert the biopsy needle. The skin edges are approximated with Steri-Strips at the end of the procedure.

Protections against risk

A number of procedures will be implemented to protect subjects against loss of confidentiality. Subjects will identify three methods to contact them for follow-up. Confidentiality will be protected in several ways during data management, processing, and analysis. The risk of disclosure of protected patient information will be minimized by the use of password protected databases behind the Mayo Clinic Health system.

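### The Risk Analysis allows the muscle biopsy from day 1, but the methods, the mitigation statement and both schedule tables set a 3-day minimum

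*Combined protocol and SAP*

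**What the plan says.** The protocol gives the timing of the biopsy in five places.

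- **Risk Analysis**, in the paragraph on how the biopsy is done: "performed at a separate visit 1-14 days after the baseline qualifying RHC".
- **Section G, Mitochondrial assessments**: "at a separate visit at least 3 days remote from the maximal exercise test".
- **Section J**, on challenges: "Additional challenges relate to the acute effects of exercise on mitochondrial respiration that may confound the biopsy results". The remedy follows in a sentence that the page break splits: "To mitigate this, the biopsy will be performed at" and then "least 3 days after the initial exercise study".
- **Schedule table for PAH-ILD subjects**: "Visit 2 Day 3-14", followed by a plus-or-minus sign with no number after it.
- **Schedule table for healthy subjects**: the same day range, with no tolerance sign.

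The biopsy is optional for patients and controls. The Expected Outcomes text for Hypothesis 1 divides patients at the median of muscle diffusion and mitochondrial indices. The corresponding text for Hypothesis 2 plans analyses stratified at the median of mitochondrial oxidative capacity.

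**The concern.** The 3-day interval is more than a scheduling convenience. Section J names it as the safeguard against carry-over from exercise into the respirometry results, and no other safeguard against that effect is stated. The Risk Analysis, which is the operational description of the biopsy (who performs it, analgesia, drug holds, aftercare), sets a lower limit that removes this safeguard for two days. Nothing in the protocol says which text prevails, so staff working from that paragraph could schedule a day-1 or day-2 biopsy without recording a deviation.

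At stake is the classification of patients as above or below the median on the mitochondrial measures. Because the biopsy is optional, the groups will be small. With 8 biopsies (an assumed number), each half would hold 4 patients, so a single misplaced patient would be a quarter of a group.

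**Working it through.** **Step 1. Do the two clocks start on different days?** The Risk Analysis counts from the baseline qualifying catheterization; the Mitochondrial assessments text and section J count from exercise. The Schedule of assessments places both in Visit 1, Day 0. The Risk Analysis says that patients qualify on the resting catheterization, and no separate earlier catheterization is scheduled. Both clocks therefore start on the same day, and the difference in anchor does not explain the difference in windows.

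**Step 2. Does anything else in the Risk Analysis restore the 3 days?** The same paragraph has a 3-day instruction about aspirin and ibuprofen. It is counted around the biopsy and concerns bleeding. It sets no interval from exercise.

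**Step 3. Count the days in conflict.**

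- Risk Analysis window: days 1 to 14, so 14 eligible days.
- Schedule tables: days 3 to 14, so 12 eligible days.
- Allowed by the first but not the second: days 1 and 2. Share = 2/14 = 14.3%.

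**Step 4. Expected number of early biopsies.** The documents give neither the number of patients who will accept the biopsy nor a distribution of visit days. I assume m = 8, 11 or 15 biopsies and consider two ways of scheduling.

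*Staff follow the schedule tables as printed (day 3 to 14):* expected number = 0 for every m.

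*Staff follow the Risk Analysis, with visit days uniform over days 1 to 14 (assumption):*

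- Expected number = m × 2/14
  - m = 8: 1.1
  - m = 11: 1.6
  - m = 15: 2.1
- Chance of at least one = 1 − (12/14)^m
  - m = 8: 0.71
  - m = 11: 0.82
  - m = 15: 0.90

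The range is therefore 0 to about 2 early biopsies. The probabilities hold only under the second way of scheduling.

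**Step 5. Which analyses use the biopsy?** The median splits by mitochondrial indices under both hypotheses use it, as do the respirometry results themselves. The paired t test on exertional cardiac output does not. Nor does the logistic regression of NYHA improvement on the change in cardiac output.

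**The case against.** The strongest reply is that the weight of the text favours 3 days. One sentence in a risk narrative stands against the methods, an explicit mitigation statement and both schedule tables. Section J supplies the floor, the anchor and the reason, and a coordinator would normally schedule from the table. This stands as a reason to expect few early biopsies, possibly none, and it is why the range must include zero. It does not remove the contradiction, because the protocol gives no order of precedence.

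A second reply is that 20 watts is too light to matter. The protocol does not support this: section G says that the workload is peak capacity for more than 90% of these patients, they perform it twice, and section J treats the exercise as a possible confounder.

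A reader might also draw stronger conclusions that the documents do not support:

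- *That early biopsies are confounded.* The protocol says only that exercise may confound them, and it gives no size for an effect on day 1 or 2. Whether any patient would cross the median is unknown.
- *That the tolerance sign in the PAH-ILD table lets the biopsy fall before day 3.* A blank tolerance authorises no particular day. The number may have been lost when the table was extracted, since the neighbouring Visit 3 column prints its tolerance in full. It is a point to confirm.
- *That the reference to a maximal exercise test leaves the floor undefined, because patients are not exercised to exhaustion.* The wording is loose, but controls do exercise to exhaustion, and section J restates the floor against the initial exercise study.
- *That the damage could not be repaired afterwards.* No repeat biopsy is scheduled, but an early biopsy can be identified from the visit dates and set aside.

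**Conclusion.** The point holds as an internal contradiction in the current text. The Risk Analysis permits biopsies on days 1 and 2; four other places do not; and those two days lie inside the interval that the protocol calls potentially confounded.

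Its size is modest: 0 early biopsies if the tables are followed, and about 1 to 2 if the Risk Analysis is followed, assuming uniform visit days and 8 to 15 biopsies. The 71% to 90% chance of at least one early biopsy rests on those same assumptions and should not be read as a forecast.

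The consequence is confined to optional, largely exploratory analyses. A reader might infer that the trial's main results are at risk. They are not, because neither the paired cardiac output comparison nor the NYHA regression uses biopsy data. The point still merits correction, because the rule as written defeats the stated mitigation and the remedy costs almost nothing.

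**What to change.** 1. Reconcile the Mitochondrial assessments text, section J, the Risk Analysis and both schedule tables to a single biopsy window, consistent with the protocol's own mitigation statement.
2. Use one named anchor throughout: the Visit 1 exercise study. This describes both the patients' 20-watt exercise and the control's exercise to exhaustion.
3. Confirm whether the tolerance sign in the PAH-ILD table carries a number of days; if it does not, complete it or delete it.
4. State in the analysis section that any biopsy taken inside the interval the protocol calls potentially confounded is reported separately and left out of the median-split analyses.

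This is wording in one amendment. The handling rule in item 4 is useful even if some biopsies have already been taken. The only downside is that an early biopsy would be lost to an exploratory analysis that is already small.
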